14.7 Sensitivity Analyses

Sensitivity analyses will include a per-protocol analysis. This will be performed on the microbiological population only and include only those who were adherent to their randomised treatment duration. Sensitivity analyses will also include an assessment around some of the assumptions made regarding missing data. An analysis of the primary outcome, where urine sterilisation is included as part of the primary outcome definition, will also be considered.

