7.1.3 Duration of cefalexin

Trial participants will be randomised to either 3 days (6 doses), 5 days (10 doses), 6 days (12 doses), 8 days (16 doses) or 10 days (20 doses) of cefalexin.

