7.4 Premature discontinuation of cefalexin

Cefalexin may be discontinued prior to a participant completing the assigned treatment course duration. Reasons for this include:

- The baseline urine culture result demonstrates a UTI caused by a cefalexin-resistant pathogen. As per standard practice, cefalexin will be discontinued and a different antibiotic with proven pathogen susceptibility will be commenced.
- The baseline urine culture result demonstrates no growth or below threshold growth. Sites will be permitted to inform families and advise discontinuation of cefalexin therapy, should this be their standard practice.
- A significant adverse reaction to cefalexin.
- Failure to tolerate oral cefalexin treatment and/or other clinical deterioration.

All such decisions are at the discretion of the treating clinician. The reason for any premature discontinuation of cefalexin will be logged on the Change of Status and Primary Outcome Assessment eCRF by the local study team.

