7.5 Extension of cefalexin course duration

After the final day of treatment, parents/guardians will be advised to obtain a medical review if they feel that their child's symptoms have not resolved. If the clinician believes the child requires additional antibiotic treatment, this will be prescribed at the clinician's discretion. Reasons for any additional non-trial antibiotics prior to the primary outcome assessment visit will be documented and logged on the Primary Outcome Assessment eCRF.

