7.7 Adherence

In contrast to trials which investigate medications in tablet form, it will not be possible to dispense a rationed volume of liquid medication appropriate for the allocated duration arm. In paediatric practice, medication suspensions are reconstituted according to the manufacturer's instructions, and any excess volume in the bottle allows for common issues of spillage or doses being spat out by the child. The dispensing of these standard volume bottles creates a potential for non-adherence with allocated cefalexin duration, and it will therefore be necessary to monitor adherence, which will

be defined as no more than one missed dose from the allocated full course, as logged on the medicine tracker page of the CURLY app, and no additional dose(s) beyond the assigned treatment duration. The app will support adherence by providing a visual prompt to parents/guardians about the duration of the allocated cefalexin, and when their child's final antibiotic dose is due.

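### The per-protocol rule drops children who fail mid-course as non-adherent, over a longer window in longer arms, so it tends to flatter longer courses

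*Protocol*

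**What the plan says.** Section 14.7 restricts the per-protocol analysis to the microbiological population and will "include only those who were adherent to their randomised treatment duration". The protocol's only definition of adherence, in section 7.7 and repeated in 8.2.1, has two parts: "no more than one missed dose from the allocated full course", and "no additional dose(s) beyond the assigned treatment duration". Section 7.1.3 sets the courses at 6, 10, 12, 16 and 20 doses.

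Three other sections bear on who meets that definition:

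- Section 7.4 lists reasons for stopping cefalexin early, among them "Failure to tolerate oral cefalexin treatment and/or other clinical deterioration".
- Section 7.5 covers the period after the course: "If the clinician believes the child requires additional antibiotic treatment, this will be prescribed at the clinician's discretion".
- Section 8.1 makes any additional systemic antibiotic prescription by day 16 a failure to cure.

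No section says that stopping because of failure, or treatment prescribed after the course, is exempt from the adherence rule. The introduction to section 14 states that the main analyses follow the allocated duration whatever the adherence.

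**The concern.** Membership of the per-protocol set depends on the outcome. A child who deteriorates and is switched with two or more doses left has failed on the primary outcome and has also become non-adherent, so the failure disappears from the analysis.

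This happens to a different extent in each arm. A child switched on day 6 is removed from the 10-day arm. The same child in the 3-day arm has already finished the course, counts as adherent, and stays in as a failure. Long arms therefore lose more of their failures than short arms, and a flat duration-response curve can look as if it rises.

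Adherence is a real worry in this trial: section 7.7 says that surplus suspension at home creates a potential for non-adherence. Readers will use the per-protocol curve as a check on the primary curve, so a slope produced by the analysis set could be read as a benefit of longer treatment.

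**Working it through.** **The plan's own figures.** The protocol gives no figure for the per-protocol analysis. The population it starts from does reproduce: 705 × 0.88 × 0.90 × 0.90 = 502.5, against the target of 500.

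**Inputs from the protocol.** Twice-daily dosing and 3 to 10 days of treatment (7.1.2, 7.1.3); at most one missed dose (7.7); additional antibiotic counted as failure (8.1); decision limit of 90% of the 10-day cure rate (14.4).

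**Assumptions.** The true failure proportion F is the same in every arm. Every failure during the course ends trial cefalexin and is rescued with a different antibiotic. No failure after the course is treated with cefalexin again. A failure is excluded if it occurs before day d − 0.5 of a d-day course. The exact cut depends on the hour of the first dose, but moving it by half a day shifts all arms alike and barely changes the ratio.

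**Formula.** If p(d) is the share of failures excluded in the d-day arm:

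- per-protocol cure = (1 − F) / (1 − F·p(d))
- 3-day/10-day ratio = (1 − F·p(10)) / (1 − F·p(3))

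**Three timings of failure.**

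- A, even over days 0-16: p(3) = 2.5/16 = 0.156; p(10) = 9.5/16 = 0.594
- B, even over days 1-16: p(3) = 1.5/15 = 0.100; p(10) = 8.5/15 = 0.567
- C, even over days 0-10: p(3) = 2.5/10 = 0.25; p(10) = 9.5/10 = 0.95

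**Per-protocol cure, 3 days v 10 days, and ratio (the true ratio is 1.00).**

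| F | A: days 0-16 | B: days 1-16 | C: days 0-10 |
|---|---|---|---|
| 10% | 91.4% v 95.7%, 0.956 | 90.9% v 95.4%, 0.953 | 92.3% v 99.4%, 0.928 |
| 12% | 89.7% v 94.8%, 0.946 | 89.1% v 94.4%, 0.943 | 90.7% v 99.3%, 0.913 |
| 15% | 87.0% v 93.3%, 0.933 | 86.3% v 92.9%, 0.929 | 88.3% v 99.1%, 0.891 |
| 20% | 82.6% v 90.8%, 0.910 | 81.6% v 90.2%, 0.905 | 84.2% v 98.8%, 0.853 |

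Across all five arms, for F = 10% under timing A, cure reads 91.4%, 92.6%, 93.2%, 94.4% and 95.7%: a steady rise where the truth is 90% throughout.

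**Where the ratio reaches 0.90.** Setting the ratio to 0.90 gives F = 0.1 / (p(10) − 0.9·p(3)).

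- A: 0.1/0.453 = 22%
- B: 0.1/0.477 = 21%
- C: 0.1/0.725 = 14%

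**If cefalexin re-treatment after the course also breaks adherence.** Let a share s of post-course failures be dropped as well. The denominator becomes 1 − F + F(1 − p(d))(1 − s). With F = 12%, timing B and s = 0.5:

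- 3 days: 0.88 / (0.88 + 0.12 × 0.900 × 0.5) = 0.88/0.934 = 94.2%
- 10 days: 0.88 / (0.88 + 0.12 × 0.433 × 0.5) = 0.88/0.906 = 97.1%

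The gap falls from 5.3 to 2.9 points and the ratio becomes 0.970. With s = 1 every failure is removed and every arm shows 100% cure.

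**If failures are kept in the set.** The flat truth is recovered: cure is 1 − F in every arm and the ratio is 1.00.

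**The case against.** Several points on the other side stand.

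- This is one sensitivity analysis. The recommended duration comes from the as-randomised curves, and no decision rule uses the per-protocol result.
- The size depends on a failure rate and timing that the protocol does not give. A child who fails through persistent fever without a switch stays adherent, which weakens the effect.
- Whether treatment after the course breaks adherence is unclear. The heading of 7.5 speaks of extending cefalexin, but its text records such prescriptions as non-trial antibiotics, and the ban on extra doses in 7.7 comes in a paragraph about leftover suspension. Where the ban does apply, it narrows the gap between arms.
- The allowance of one missed dose is 1/6 = 16.7% of the shortest course and 1/20 = 5% of the longest. Missed doses unrelated to outcome reduce numbers unequally, but do not by themselves create a false difference in cure.

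A reader might infer that the per-protocol analysis can neither confirm nor challenge the primary result, or that it would falsely support shortening. The documents do not support either reading. The likely distortion is against short courses, so a per-protocol result that still favoured a short course would remain informative. With 10-15% failure spread over about 16 days, the expected ratio also stays above 0.90.

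The argument that this belongs to the statistical analysis plan stands only in part. Section 14 is a brief overview, but the protocol already fixes both the restriction to adherent children and the definition of adherence. A plan that follows them literally inherits the problem.

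**Conclusion.** The point holds for the per-protocol sensitivity analysis. As written, the adherence rule removes children because they failed during the course, and does so over about 3 days in one arm and about 10 in another. With a flat truth this tends to make longer courses look better.

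For 10-15% failure spread over about 16 days, with rescue by a different antibiotic, the expected 3-day/10-day cure ratio is about 0.93-0.96 instead of 1.00. Under that timing it crosses 0.90 only when failure exceeds about 20%; if all failures fall in days 0-10, it crosses at about 14%. Counting post-course cefalexin as extra doses removes more failures from every arm and shrinks the gap. These figures illustrate the mechanism and do not predict the trial's result. The primary and intention-to-treat analyses are unaffected.

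**What to change.** Define the per-protocol set separately from the adherence outcome, in section 14.7 or in the statistical analysis plan:

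- Judge adherence only up to the earlier of the end of the allocated course and primary-outcome failure.
- Keep children whose cefalexin was stopped by a clinician because of failure, or who were prescribed an antibiotic after the course, in the set as failures.
- Exclude only under-dosing or over-dosing initiated by the family before failure.
- State whether cefalexin prescribed after the course counts as an additional dose, so that 7.5 and 7.7 agree for analysis purposes.

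The cost is wording, best settled before outcome data are examined. Reasons for stopping (7.4), reasons for additional antibiotics (7.5) and the app dose log (9.1.3) are already collected. The change concerns membership of the analysis set and alters no clinical rule. Reporting adherence also as the proportion of allocated doses taken is optional and not needed to correct the error.

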14.8 Planned final analyses

The primary analysis for the trial will occur once all participants have completed the remote followup for recurrence at 30 days post-randomisation, the results of microscopy, culture and antibiotic sensitivity for this follow-urine sample have been reported, and the corresponding outcome data and results have been entered onto the trial database and validated as being ready for analysis.

15. HEALTH ECONOMICS

A separate Health Economics Analysis Plan will be produced and will provide a more comprehensive description of the planned analyses. A brief outline of these analyses is given below.

15.1 Within-trial economic evaluation

The base-case cost-effectiveness analysis will be conducted from an NHS/personal social services (PSS) perspective. A cost-consequences analysis will initially be reported, describing all the important results relating to costs and outcomes. Subsequently, an incremental cost-utility analysis will be undertaken to calculate a cost per quality-adjusted life year (QALY) gained over the follow-up period. To obtain QALYs, utility data will be estimated using the CHU9D questionnaire. Where appropriate, this will be self-completed (typically by children over 7 years of age). Proxy versions of the CHU9D will be used for younger children and for those lacking understanding. The proxy version can also be used for children over 7 years of age if they require parental assistance. The resulting descriptive profiles will be converted into utility values using the UK tariff (40).

Health service resource use will be collected using standard data collection forms and unit cost data will be derived from nationally represented sources such as the BNFC, the National Schedule for Reference Costs and the Unit Costs of Health and Social Care.

The incremental cost and benefit of the treatment durations will be estimated over the follow-up period. In accounting for the novel trial design, the various treatment durations will be compared incrementally with the optimal duration and the most cost-effective treatment duration will be determined using the principles of dominance and extended dominance. Results will be expressed as incremental cost-effectiveness ratios (ICERs) using ICER plots and cost-effectiveness acceptability curves to represent the probability of the treatment durations being cost-effective at different willingness to pay thresholds. Appropriate sensitivity analysis will be applied to explore how sensitive the results are to data parameters and assumptions within the analyses. A secondary analysis will adopt a wider societal perspective which would account for the effect of treatment

duration on nursery/school days missed and resulting parental leave from work, along with the cost of antimicrobial resistance. The approach to capturing the costs of antimicrobial resistance would be similar to those adopted in previous literature (44, 45). This would involve estimating costs of resistance associated with antibiotic use and adding this to the costs of each patient in the study based on their antibiotic use.

16. TRIAL ORGANISATIONAL STRUCTURE

16.1 Sponsor

The Sponsor for this trial is the University of Birmingham.

16.2 Coordinating centre

The trial coordinating centre (Trial Office) is Birmingham Clinical Trials Unit, based at the UoB.

16.3 Trial Management Group

The Trial Management Group (TMG) comprises individuals responsible for the day-to-day management of the trial: the CI, co-lead, Trial Manager, Trial Statistician and senior BCTU oversight staff. The role of the group is to monitor all aspects of the conduct and progress of the trial, ensure that the protocol is adhered to and take appropriate action to safeguard participants and the quality of the trial itself. The TMG will meet sufficiently frequently to fulfil its function.

16.4 Co-investigator group

The Co-investigator group, an extended TMG, will comprise all members of the co-applicant group and the members of the TMG to review progress, troubleshoot and plan strategically.

16.5 Trial Steering Committee

A Trial Steering Committee (TSC), comprising independent and non-independent members, will be established for the CURLY trial and will meet as required depending on the needs of the trial. The TSC will be chaired by an independent member; membership, duties and responsibilities are outlined in the TSC Charter. In summary, the role of the TSC is to provide oversight of the trial. The TSC will monitor trial progress and conduct and provide advice on scientific credibility. The TSC will consider and act, as appropriate, upon the recommendations of the Data Monitoring Committee (DMC). The TSC will operate in accordance with a trial specific TSC Charter.

16.6 Data Monitoring Committee

The role of the independent DMC is to monitor the trial data and make recommendations to the TSC on whether there are any ethical or safety reasons as to why the trial should not continue or whether it needs to be modified. To this end, data on safety outcomes and (where appropriate) primary and secondary outcomes will be supplied to the DMC during the trial. Reports will be supplied in confidence. The DMC will operate in accordance with a trial specific DMC Charter which will define the membership, roles and responsibilities of the DMC. The DMC will meet at least annually as a minimum. Additional meetings may be called if needed.

16.7 Finance

The research costs of the trial are funded by the National Institute for Health and Care Research (NIHR) Health Technology Assessment (HTA) programme awarded to [name] at the Birmingham Women's and Children's NHS Foundation Trust.

17. ETHICAL CONSIDERATIONS

The trial will be conducted in accordance with the UK Policy Framework for Health and Social Care Research and applicable UK Acts of Parliament and Statutory Instruments (and relevant subsequent amendments), which include, but are not limited to, the Medicines for Human Use (Clinical Trials) Regulations 2004, Human Tissue Act 2004 and the Data Protection Act 2018.

This trial will be carried out under a Clinical Trial Authorisation in accordance with the Medicines for Human Use Clinical Trials regulations and according to the Principles of GCP as set out in the UK Statutory Instrument (2004/1031; and subsequent amendments)⁸.

The protocol will be submitted to and approved by the REC prior to the start of the trial. All correspondence with the MHRA and/or REC will be retained in the TMF/ISF, and an annual progress report will be submitted to the REC within 30 days of the anniversary date on which the favourable opinion was given by the REC, and annually until the trial is declared ended. A trial-specific risk assessment and monitoring plan will be developed before submission to the REC and will be reviewed regularly during the trial.

Before any participants are enrolled into the trial, the PI at each site is required to obtain the necessary local approval.

It is the responsibility of the PI to ensure that all subsequent amendments gain the necessary local approval. This does not affect the individual clinicians' responsibility to take immediate action if thought necessary to protect the health and interest of individual participants.

This is a randomised controlled trial therefore neither the parents/guardians nor the physicians will be able to choose the child's treatment.

There will be one additional hospital visit for children in the trial. Other additional contacts will be performed remotely, where possible, using the CURLY app or via email/SMS/telephone. All participants will receive reimbursement of follow-up visit travel expenses, along with a £20 voucher of appreciation for their time contributing to study data collection.

18. DATA PROTECTION AND CONFIDENTIALITY

Personal data recorded on all documents will be regarded as strictly confidential and will be handled and stored in accordance with the Data Protection Act 2018 (and subsequent amendments)⁹.

Participants will only be identified by their unique trial identification number and initials on correspondence with the Trial Office. For all participants full name, full date of birth, gender and NHS number will be collected on the Randomisation Form. The participant's full name will also be collected on the participant consent forms, in addition to their parents'/guardians' email address and/or mobile number. Participants and parents/guardians will give their explicit consent for the

⁸ Ireland: In compliance with applicable EU and Irish regulations.

⁹ Ireland: In compliance with the equivalent EU and Irish regulations.

storage of their consent form on the trial database held on secure servers controlled by the University of Birmingham. This will be used to perform in-house monitoring of the consent process.

The PI must maintain documents not for submission to the Trial Office (e.g. Participant Recruitment and Identification Logs) in strict confidence. In the case of specific issues and/or queries from the regulatory authorities, it will be necessary to have access to the complete trial records, provided that participant confidentiality is protected.

BCTU will maintain the confidentiality of all participant data and will not disclose information by which participants may be identified to any third party. Representatives of the Trial Office and Sponsor may be required to have access to participants' notes for quality assurance purposes, but participants should be reassured that their confidentiality will be respected at all times.

19. FINANCIAL AND OTHER COMPETING INTERESTS

There are no financial or other competing interests related to the results of this trial. Members of the TSC and DMC are required to provide declarations on potential competing interests as part of their membership of the committees. Authors are similarly required to provide declarations at the time of submission to publishers.

20. INSURANCE AND INDEMNITY

The UoB has in place Clinical Trials indemnity coverage for this trial which provides cover to UoB for harm which comes about through the University's, or its staff's, negligence in relation to the design or management of the trial and may alternatively, and at UoB's discretion provide cover for non-negligent harm to participants.

With respect to the conduct of the trial at Site and other clinical care of the patient, responsibility for the care of the patients remains with the NHS organisation responsible for the Clinical Site and is therefore indemnified through the NHS Litigation Authority¹⁰.

21. POST-TRIAL CARE

Following completion of the trial, patients will be managed according to the standard clinical care that is deemed appropriate by their treating clinician(s).

22. ACCESS TO FINAL DATASET

The final dataset will be available to members of the TMG and co-applicant group who need access to the data to undertake the final analyses.

Requests for data generated during this study will be considered by BCTU. Only scientifically sound proposals from appropriately qualified research groups will be considered for data sharing. The request will be reviewed by the BCTU Data Sharing Committee in discussion with the CI and, where appropriate (or in the absence of the CI) any of the following: The Trial Sponsor, the relevant TMG members, and independent TSC.

¹⁰ Ireland: State Claims Agency clinical trial indemnity scheme.

A formal Data Sharing Agreement (DSA) may be required between respective organisations once release of the data is approved and before data can be released. Data will be fully de-identified (anonymised) unless the DSA covers transfer of patient identifiable information. Any data transfer will use a secure and encrypted method.

23. PUBLICATION POLICY

The trial publications will be prepared by the co-investigator writing group at the completion of the trial, as defined in the trial publication plan. All manuscripts will be submitted to the TMG in a timely fashion and in advance of being submitted for publication to allow time for review. No patient/parent/guardian identifiable information will be contained in any form of dissemination of study results.

In all publications, authors will acknowledge that the trial was performed with the support of the NIHR, UoB, BCTU and PERUKI. Intellectual property rights will be addressed in the Site Agreement between Sponsor and site.

Dissemination will be *via* traditional and novel methods as discussed below.

